 - 1. Demonstrate an improvement in speech perception abilities in an aided (cochlear implant on) versus an unaided (cochlear implant off) condition
 - 2. Demonstrate an improvement in localization abilities in an aided (cochlear implant on) versus an unaided (cochlear implant off) condition
 - 3. Demonstrate an improvement in subjective report in an aided (cochlear implant on) versus an unaided (cochlear implant off) condition

VIII. Statistical Analysis

- A. Descriptive summaries will be provided for the following: subject demographics, and frequency of major and minor complications/adverse events.
- B. A single-subject design will be utilized, where each subject serves as his or her own control, for analysis of objective and subjective results. A singlesubject design was chosen in order to accommodate the heterogeneity that is well known to characterize auditory prosthesis research. Repeated-measures ANOVA will be calculated with a p-value of ≤ 0.05 for statistical significance. Statistical analysis will be conducted with SPSS software.
 - 1. Comparison in aided speech perception performance on word and sentence materials in the post-initial activation intervals
 - a. Also compare the difference between the aided and unaided conditions at each follow-up interval
 - 2. Comparison in localization abilities in the post-initial activation intervals
 - a. Also compare the difference between the aided and unaided conditions for each follow-up interval
 - 3. Comparison in subjective report in the post-initial activation intervals

If needed, statistical consultation will be sought from the North Carolina Translational and Clinical Sciences Institute (TraCS) or UNC Odum Institute.

IX. Endpoints

- A. Safety endpoint
 - 1. The primary safety endpoint is the evaluation of Adverse Events. All Adverse Events will be reported to the UNC IRB. If the UNC IRB or study investigators deem an Adverse Event unacceptable, then this would be sufficient terms to terminate the study.
- B. Primary effectiveness endpoint

1. The primary effectiveness endpoint is the comparison of speech perception (VII.A.1), localization abilities (VII.A.2) and/or subjective report (VII.A.3) when the cochlear implant is on versus off.

X. Risk Analysis

A. Potential risks

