 - 3. Reports of pain from the external speech processor placement will be addressed by different wearing options (i.e. moleskin between the external speech processor and the subject's ear, or different battery-wearing options to lighten weight on the pinna).
 - 4. Mapping will be conducted at each post-initial activation interval to improve audibility and comfort of the sound quality from electric stimulation.
 - 5. The MED-EL cochlear implant has MRI limitations*. Subjects may have CT scans or x-ray imaging postoperatively.
 - a. *The MED-EL SYNCHRONY cochlear implant is approved for MRI up to 3 Tesla with the magnet in place (magnet can be removed to eliminate shadow if necessary).
 - 6. An otologist will conduct medical follow-up evaluations at the 3, 6 and 12-month intervals which is standard of care for cochlear implant recipients.

XI. Potential Benefits

- A. Improvement in speech perception abilities in noise with the cochlear implant due to utilization of auditory cues from both ears.
- B. Improvement in localization abilities with the cochlear implant due to utilization of auditory cues from both ears.
- C. Improvement in subjective benefit with the cochlear implant as compared to an unaided condition.

XII. Adverse Events

A. Anticipated versus Unanticipated Events

- 1. Anticipated Events: those events described as potential risks (section X.A.) of the protocol.
- 2. Unanticipated Events: events not reported as potential risks (section X.A.).
 - a. Unanticipated serious adverse events are defined as any serious adverse event related to the health or safety or any life-threatening problem or death caused by, or associated with, a device, if that event, problem, or death that was not previously defined in nature, severity, or degree of incidence in the literature or investigational plan. It can also include any other unanticipated serious problem associated with a device that relates to the rights, safety or welfare of subjects.
- B. Reporting adverse events
 - 1. Anticipated events will be reported to the FDA in the annual report
 - 2. Unanticipated events will be reported to the FDA and UNC IRB within 10 days of the investigator becoming aware of the event, as required by 21CFR 812.150.

XIII. Monitoring

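### The primary effectiveness endpoint (IX.B.1) names no measure, visit or success rule, its on/off tests are unadjusted at 0.05, and its subjective component has no on/off analysis

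*Combined protocol and SAP*

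**What the plan says.** The primary effectiveness endpoint in IX.B.1 is "the comparison of speech perception (VII.A.1), localization abilities (VII.A.2) and/or subjective report (VII.A.3) when the cochlear implant is on versus off". The section does not say which score, listening condition or visit is meant, or how many of the three domains must succeed.

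VIII.B sets one threshold: "Repeated-measures ANOVA will be calculated with a p-value of ≤ 0.05 for statistical significance". For speech, VIII.B.1.a adds: "Also compare the difference between the aided and unaided conditions at each follow-up interval". For localization, VIII.B.2.a adds: "Also compare the difference between the aided and unaided conditions for each follow-up interval". There are five visits (1, 3, 6, 9 and 12 months, VI.C). No adjustment, hierarchy or gatekeeping appears anywhere.

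For subjective report, VIII.B.3 lists only this: "Comparison in subjective report in the post-initial activation intervals". Yet the claim in VII.A.3 is "Demonstrate an improvement in subjective report in an aided (cochlear implant on) versus an unaided (cochlear implant off) condition", and XI.C anticipates "Improvement in subjective benefit with the cochlear implant as compared to an unaided condition".

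V.C and VI.B.4.g call 12 months the study endpoint, but neither IX.B.1 nor VIII.B ties the primary comparison to it. The planned sample is 10 subjects (VI.A.3), with no effect size, SD or power given.

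**The concern.** VII.A sets out to demonstrate effectiveness, but the 0.05 in VIII.B applies to each test and not to that claim. The and/or wording leaves open whether one positive domain is enough or all must be positive. Within a domain, nothing says which of many scores decides. If any one significant result suffices, the chance of supporting the claim when the implant does nothing exceeds that of a single test.

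Two further gaps affect what is being tested.

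- **Speech contrast.** VI.C.3.b.iii has two conditions with the processor on: implant only with the other ear masked, and Combined. Only Combined against Contralateral ear only changes the processor state and nothing else. It is also the contrast that matches XI.A: "Improvement in speech perception abilities in noise with the cochlear implant due to utilization of auditory cues from both ears".
- **Subjective report.** One of the three primary components has no matching on/off analysis.

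**Working it through.** **The plan's own figure.** There is none to reproduce beyond the 0.05 per test. The plan gives no familywise rate, and N = 10 has no derivation.

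**Count of on/off outcomes per visit (VI.C.3).** This takes one processor-on condition and one SNR per material.

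- Quiet: 4 materials, of which HINT and AzBio are conditional.
- Noise: 3 materials × 3 noise positions = 9.
- Localization: 2 scores (error, adjusted constant error).
- Total: 4 + 9 + 2 = 15.

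A second processor-on condition for speech, or extra SNR steps, would add more.

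**Independent tests.** The chance of at least one p ≤ 0.05 under no effect is 1 − 0.95^k. For k = 2 it is 1 − 0.9025 = 9.75%. Counting only results in the implant's favour, it is 1 − 0.975² = 4.9%.

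**Correlated tests.** These were simulated with n = 10 and paired t-tests. For two conditions a paired t is the same test as a repeated-measures ANOVA (F = t²). The on/off main effect over five visits equals a paired t on visit averages. Assumed correlations, not in the documents: 0.3–0.9 between outcomes and 0.5–0.9 between visits.

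| Family of tests | Any p ≤ 0.05, two-sided | In the implant's favour |
|---|---|---|
| Single test | 5% | 2.5% |
| 2 measures, one visit | 7.3–9.6% | 3.6–4.8% |
| 2 measures × 5 visits | 15–34% | 8–17% |
| 15 outcomes, one visit | 16–47% | 8–25% |
| 2 measures, main effect over visits | 7.2–9.6% | 3.6–4.8% |
| 15 outcomes, main effect over visits | 16–48% | 8–25% |

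**Rules that hold the error.** These are for two named tests, with correlation 0–0.9 and no effect. Holm gives a familywise rate of 3.8–4.9%. Requiring both at 0.05 gives 0.3–2.8%.

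**Power at n = 10.** A single test uses the noncentral t with 9 df and noncentrality d√10, where d is the assumed paired difference in SD units. The Holm and both-required columns assume both domains at d, with correlation 0–0.9.

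| d | Single test, 0.05 | Single test, 0.025 (Holm first step) | Holm, per domain | Both required at 0.05 |
|---|---|---|---|---|
| 0.8 | 62% | 47% | 53–54% | 38–54% |
| 1.0 | 80% | 68% | 73–76% | 64–75% |
| 1.2 | 92% | 84% | 88–91% | 85–89% |

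In a fixed order, the first domain has the single-test power and the second has the both-required power. At d = 1.0, Holm gives 75–90% for at least one domain.

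**Subjective report, passages side by side.** VII.A.3 and IX.B.1 call for on versus off, and XI.C for a comparison with an unaided condition. VIII.B.3 compares visits only. VI.C.4 lists SSQ and APHAB without describing an implant-off administration. Appendix B schedules questionnaires only at 1–12 months after activation, so no preoperative score could stand in.

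**The case against.** - **The visit is named elsewhere.** V.C and VI.B.4.g give 12 months as the study endpoint. If that governs, the five-visit rows of the first table fall away. The choice of measure and domain stays open, and VIII.B still orders tests at every visit.
- **Only improvement supports the claim.** VII.A speaks of improvement, so the favourable-direction column is the relevant one. With just two measures at one visit it stays below 5%. This stands for that minimal case, although the rate is still above the 2.5% of one two-sided test. Nothing limits the plan to two measures.
- **The domains may be three separate claims, or all may be required.** Either reading removes the need to adjust across domains, and requiring all on one fixed test each would need no adjustment at all. The text adopts neither reading. Separate claims would still leave up to 13 speech outcomes and 2 localization outcomes to choose from.
- **Quiet testing may not be where benefit is expected.** Subjects must have good contralateral hearing (VI.A.1), and XI.A places the benefit in noise. Dropping the quiet materials leaves 11 outcomes: 14–39% two-sided, 7–20% in the implant's favour. The problem is smaller but remains.
- **VIII.B applies the own-control design to subjective results too.** It does, but VIII.B.3 lists no on/off comparison and no implant-off questionnaire is described. This gap is not answered.

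**Conclusion.** The concern holds and must be fixed. Success on the primary effectiveness endpoint is undefined, and the stated per-test rule does not show that the effectiveness claim is held at 5%.

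The inflation applies only if one significant result is enough. Its size runs from slight, with two measures at 12 months, to several times nominal across the listed battery. It depends on the assumed correlations and on the count of 15, which is one reading. The missing measure, success rule and speech contrast rest on the text alone. So does the lack of an on/off analysis for subjective report.

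**What to change.** In IX.B.1 and VIII.B:

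1. Name one speech-in-noise score in one noise position and one of the two localization scores. The choice is the sponsor's. BKB-SIN is one candidate, because under the >50% stepping rule HINT and AzBio could be scored at different SNRs on and off.
2. Define each as the within-subject difference, Combined minus Contralateral ear only, at 12 months.
3. State the success rule. One option claims each domain whose Holm-adjusted two-sided p ≤ 0.05 across the two, which fits the and/or wording. The others are testing the two at 0.05 in a fixed order set in advance, or requiring both at 0.05.
4. Reconcile VII.A.3, IX.B.1 and XI.C with VIII.B.3. Either take subjective report out of the on/off primary, or describe how SSQ and APHAB are answered for the implant-off condition, add that analysis and include it in the adjustment.
5. Report the other outcomes and the 1, 3, 6 and 9-month contrasts descriptively with confidence intervals.

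**Cost.** If subjective report leaves the on/off primary, this is an amendment to wording only (VII.A.3, VIII.B, IX.B.1, XI.C), because speech and localization are already collected in both conditions at 12 months. If it stays, an implant-off administration must be added. The claim becomes narrower, and the planned tests at earlier visits become descriptive. The power cost depends on the rule chosen. Requiring both costs the most if the two domains are weakly correlated.

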- A. Subjects will be monitored on a case-by-case basis for ongoing or unanticipated medical complications. Adverse events will be tracked on a case-by-case basis and recorded in study binders at the time of occurrence and followed up at resolution. Any adverse event will be reported to the UNC IRB. Should there be concern for the safety of subjects because of their participation in the study by the investigators or the UNC IRB, the study would be halted at least temporarily and a detailed discussion with the investigators and UNC IRB would be undertaken to evaluate the viability of the study.
- B. Subjects can withdraw from the study at any time by notifying the Primary Investigator. If the investigator identifies the need to withdraw a subject from the study for any reason, this will be discussed in person during a scheduled evaluation. In either scenario, the subject will continue to receive care irrespective of their participation in the study. Should a subject not be able to receive auditory stimulation from the cochlear implant, or develops a complication related to participation in the study, their participation in the study will end when their study related morbidity has resolved or is no longer active. Again, this will not affect the medical care for the subject.

XIV. Confidentiality

A. Subjects will be assigned a specific, anonymous subject number that will be associated with his or her data. Database entry will be by subject number

only. All personal identifiers will be kept in a separate, secure data file that will be password protected and not associated with the study data. Only investigators will have access to the subject numbers.

- B. Subject specific binders will be maintained in a locked cabinet in the Carolina Crossing research lab. Individual data collection sheets will be coded with the subject number and placed in the subject specific binder at each interval. For analysis, the data will not included identifiable information.
- C. Data will not be shared outside the investigative team except during reporting of anonymous results.
- D. After the closure of the study, subject data will be retained for seven years. At that time, paper data will be shredded and destroyed in a HIPAA compliant manner. Electronic data will be destroyed following UNC policy.
- E. A description of the clinical trial will be available on http://ClinicalTrials.gov. This web site will not include information that can identify research subjects.

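### Participation ends for subjects who get no auditory stimulation, and Section VIII has no analysis set or score for them; if one occurs, mean on/off benefit would normally describe stimulated subjects only

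*Combined protocol and SAP*

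**What the plan says.** Section XIII.B (Monitoring) sets an exit rule with two triggers: "Should a subject not be able to receive auditory stimulation from the cochlear implant, or develops a complication related to participation in the study". The consequence is that "their participation in the study will end when their study related morbidity has resolved or is no longer active". The next sentence, "Again, this will not affect the medical care for the subject", concerns care and not data. Section X.A.2.d lists absence of any auditory stimulation among the potential risks, with no rate.

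Section VIII.B describes the analysis: "A single-subject design will be utilized, where each subject serves as his or her own control", and "Repeated-measures ANOVA will be calculated with a p-value of ≤ 0.05 for statistical significance". For speech perception, item 1.a adds: "Also compare the difference between the aided and unaided conditions at each follow-up interval". Item 2.a does the same for localization. Section IX.B defines the primary effectiveness endpoint as performance and/or subjective report "when the cochlear implant is on versus off". Section VIII gives no analysis set, no missing-data rule and no score for a subject without stimulation. Section VIII.A promises a descriptive summary that includes "frequency of major and minor complications/adverse events".

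Under Section VI.C and Appendix B, speech, localization and questionnaires are first collected 1 month after initial activation, then at 3, 6, 9 and 12 months. Section V.C makes month 12 the study endpoint. Section VI.A.3 plans ten subjects.

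**The concern.** The exit is triggered by the outcome. A subject whose implant gives no sound gains nothing from switching it on, so the true on-minus-off difference is zero. If that subject leaves before month 1 there is no on/off pair at all; if later, there is none after exit. The own-control design cannot help where no pair exists. Subjects who hear but perform poorly (X.A.2.e and f) are not caught by this trigger and stay in. The non-stimulation exit therefore takes out zeros and leaves the rest.

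Section VII.A claims effectiveness in the populations deafened by these operations, and the Introduction makes the expected benefit conditional on the auditory nerve transmitting the signal. Whether it does is part of the question. A mean over stimulated subjects takes the answer for granted. At stake are the size of the reported benefit and the population it describes.

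**Working it through.** The plan has no effect size, SD, power or failure rate, so there is no figure of its own to reproduce. The only inputs from the documents are 10 subjects (VI.A.3) and p ≤ 0.05 (VIII.B). Everything else below is assumed.

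**Overstatement.** Let n subjects be implanted, f of them without stimulation (difference 0), and let the others have mean benefit m > 0. The all-implanted mean is m(n − f)/n. The mean without the f subjects is m. Relative overstatement = n/(n − f) − 1.

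- n = 10: f = 1 gives 10/9 − 1 = 11.1%; f = 2 gives 10/8 − 1 = 25.0%; f = 3 gives 10/7 − 1 = 42.9%.
- n = 8 (if some enrolled subjects are not implanted): f = 1 gives 8/7 − 1 = 14.3%; f = 2 gives 8/6 − 1 = 33.3%.

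**How likely.** With an assumed per-subject rate r, P(at least one of 10) = 1 − (1 − r)^10, P(exactly one) = 10r(1 − r)^9, and P(two or more) is the difference.

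| Assumed r | At least one | Exactly one | Two or more |
|---|---|---|---|
| 1% | 9.6% | 9.1% | 0.4% |
| 2% | 18.3% | 16.7% | 1.6% |
| 5% | 40.1% | 31.5% | 8.6% |
| 10% | 65.1% | 38.7% | 26.4% |

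At each of these rates, if the event occurs at all, one subject is the commonest count. The 11% figure is the usual one; 25% and 43% are less likely cases.

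**Effect on the test.** Take a paired t-test with mean m and SD 1 in stimulated subjects and n = 10. With the f zeros included, the mean is m(10 − f)/10 and the variance is [(10 − f − 1) + f(10 − f)m²/10]/9.

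- m = 1.0, f = 2. Left out: 1.00, 95% CI 0.16 to 1.84, p = 0.026. Included: mean 0.80, variance (7 + 1.6)/9 = 0.956, SD 0.978, 95% CI 0.10 to 1.50, p = 0.029.
- m = 0.8, 0.9, 1.0 and 1.5 with f = 1, 2 and 3: p stays on the same side of 0.05 in all 12 combinations.
- m = 0.95, f = 3. Left out: t = 0.95 × √7 = 2.51 on 6 df, p = 0.0457. Included: mean 0.665, variance (6 + 1.895)/9 = 0.877, SD 0.937, t = 2.25 on 9 df, p = 0.0514. The conclusion changes.

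Leaving out the zeros raises the mean but also reduces n, and the two nearly cancel in t. Significance therefore rarely changes, but it can near the threshold.

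**The case against.** **XIII.B does not exclude anyone's data.** A reader might infer that the plan deliberately drops these subjects. The documents do not support that: XIII.B ends participation and is silent on data, and VIII.B does not specify complete cases. The defect is a missing rule. What stands is the practical result: without a rule, a subject with no pair at a visit contributes nothing there.

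**The exit may not be early.** If non-stimulation itself counts as morbidity, the subject might stay in follow-up. X.B.4 also plans mapping at every interval, so a month-1 on/off pair may exist. The text allows both readings. A rule that fills only visits without data works under either.

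**The event may never occur, and would be seen if it did.** Section VI.B.3.a makes structural preservation of the nerve a prerequisite for implantation in schwannoma subjects, which should lower the chance. Non-stimulation is an anticipated event under XII.A.1, so the summary in VIII.A should count it. Both points hold. But an intact structure does not guarantee function, X.A.2.d lists the risk without restricting it by etiology, and a count of events does not enter the effectiveness mean.

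**Exits are not all of one kind.** A reader might infer that every early exit inflates the benefit. That goes too far. The same sentence covers complications in subjects who may hear well, and XIII.B allows voluntary withdrawal. The direction for those is unknown.

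**Zero is an assumption.** With no sound from the implant, combined listening should equal contralateral-ear listening, so zero is the natural expected difference. A fixed zero lacks test-retest noise and slightly understates the spread. It would also be wrong for a failed device that is later revised (X.A.2.n) and works again, so that case needs an exception.

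**Conclusion.** The concern holds as a conditional one. If an implanted subject receives no stimulation and leaves, the analysis in VIII.B has no stated place for that subject. The mean on/off benefit would then normally describe stimulated subjects, and would exceed the all-implanted mean by about 11% for one such subject in 10. This rests on a zero difference without stimulation, a positive mean benefit in the others, and no other selective exit.

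Two inferences should be avoided. One is that the trial would reach a false positive through this route: in the cases checked p barely moves. The other is that significance is immune: the example with p = 0.0457 against 0.0514 shows otherwise. The main harm is to the size of the benefit and the population it is claimed for. The rule should be set before data are seen, because with ten subjects a later choice could be guided by the result.

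**What to change.** In Section VIII:

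1. Define the effectiveness set for the on/off contrast as all implanted subjects. For a subject with no auditory stimulation, set the on-minus-off difference (combined minus contralateral ear only) to zero for speech and localization at visits without data. Impute the difference, not score levels. Add a sensitivity analysis on observed data only. Impute no zeros for subjects who exit for other reasons but hear with the implant, and none after a failed device has been revised and stimulation restored.
2. Report the number and proportion of implanted subjects with stimulation, with an exact 95% confidence interval (for example, 9 of 10 gives 55% to 100%, and 8 of 10 gives 44% to 97%). List non-stimulated subjects with reason and visit of exit. State that implant-only scores, across-visit aided scores and questionnaires describe stimulated subjects only.

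The exit rule in XIII.B stays as it is. The cost is a few sentences, with no added visit or test. The downsides are a less favourable mean if an implant gives no stimulation, and reliance on an assumed zero without test-retest noise, which is why the observed-data analysis should sit beside it.
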